Interim Monitoring Procedures. On a monthly basis, the PI will produce interim reports specifically focusing on missing data and entry errors. The progress of the study will be monitored biannually by the college DSMC. On a biannual basis, the PI will prepare a written report on the progress of the study that will include data on: enrollment, comparison of target to actual enrollment, information on race, ethnicity, sex, overall status of the study participants, protocol deviations, and adverse or serious adverse events. These data will be collected in a spreadsheet format and reviewed by [name] (Study PI). All reports will be reviewed by the DSMC on a biannual basis. After each report is reviewed, the Committee will recommend whether the study should continue, continue with modifications, or be terminated. PI reports and minutes from DSMC meetings will also be sent to the Office of Responsible Research Practices. Co-I [name], who has extensive

experience with DSMCs and the conduct of clinical trials, will assist the PI in developing these reports.

Procedures for Adverse Events

Identification of adverse events. Study staff will be at the bedside during infant data collection and will record the occurrence of adverse events in real time. Adverse events (AEs) will be reported immediately to the PI. Adverse events may also be identified by parents or neonatal intensive care unit staff, who are encouraged to alert the PI of these events. During the consent process, participating nurses and parents of participating infants will be informed of the minimal risk nature of this study and encouraged to report any AEs immediately to study staff. The PI will maintain an electronic record of AEs and will include a description of AEs in the written report submitted biannually to the DSMC. Given the short-term duration of infant participation in the study, AEs will be tracked from the time that infant participation begins following the attachment of sensors for data collection and will continue until the end of the recovery period (i.e. 30 minutes after the final direct touch of the care episode).

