Definitions. **Adverse Event:** Any unfavorable and unintended sign, regardless of whether it is considered related to the intervention; also an “unanticipated problem” of any nature (e.g., psychological or social harm; designated as unrelated, definitely related, probably related, or possible related; see below). **Serious adverse event (SAE):** Any adverse event that is fatal or life threatening, is permanently disabling or requires prolongation of hospitalization. **Life-threatening event:** Any adverse event in which the subject is at immediate risk of death from the reaction as it occurs; does not include a reaction that, if it were to occur in a more serious form, might cause death. **Unexpected event:** Any adverse event that is not identified in nature, severity, or frequency in the study protocol or consent or the event was more serious than anticipated. **Definitely Related:** An adverse event that has a timely relationship to the administration of the investigational study procedure and follows a known pattern of response for which no alternative cause is present. **Probably Related:** An adverse event that has a timely relationship to the administration of the investigational study procedure and follows a known pattern of response, but for which a potential alternative cause may be present. **Possibly Related:** An adverse event that has a timely relationship to the administration of the investigational study procedure and follows no known pattern of response, but a potential alternative cause does not exist. **Unrelated:** An adverse event for which there is evidence that it is definitely related to a cause other than the investigational study procedure; in general no timely relationship to the administration of the procedure exists, or if so, the event does not follow a pattern of response and an alternative cause is present.

Grading scale for adverse event severity. **Mild:** Transient bradycardia (defined by clinical parameters established for each patient, usually heart rate <100 beats per minute), apnea, or oxygen desaturation requiring no intervention or an increase in supplemental oxygen. Bradycardia and oxygen desaturation are defined by clinical parameters established for each patient, usually heart rate <100 beats per minute or oxygen saturation <85% lasting 10 seconds. Erythema resulting from monitoring electrodes. **Moderate:** Bradycardia, apnea, or oxygen desaturation requiring an

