increase in respiratory support (i.e. hand-bagging). Epidermal stripping (i.e. non-intact skin) resulting from monitoring electrodes. Severe: Physiologic decompensation requiring intubation or cardiopulmonary resuscitation.

Review of adverse events. The study investigators will provide an initial review of all AEs to the DSMC to determine their relatedness to the research and preliminary grading of severity. For each AE, the PI will record the onset, duration, intensity, treatment required, outcome and action taken. SAEs are not expected to occur during this study. Possibly, probably, or definitely related AEs, as determined by the study team, will be reported within 24 hours to the DSMC chair for further review. The DSMC will make the final determination on AE severity and relatedness.

Reporting of adverse events. Final evaluation of relatedness and severity of AEs will be determined by the DSMC. In accordance with NCH IRB Adverse Event Reporting Policy, an AE is reportable to the IRB within 5 business days if it meets all of the following criteria: (1) the event is unexpected, (2) the event is related or probably related to study participation, and (3) is serious and/or suggests that the research places subjects or others at a greater risk of physical or psychological harm than was previously known or recognized. Additionally, per NCH IRB policy, all protocol deviations or violations that harmed participants or indicate that others might be at increased risk of harm, breaches of confidentiality, and new literature that may affect willingness to participate are reportable events within 5 business days. AEs that must be reported annually with continuing review include: (1) minor protocol deviations that do not indicate an increased risk of harm, and (2) AEs that are not serious or unexpected. After review by the DSMC, all reportable AEs will be submitted by the PI to the NCH IRB. Reportable AEs will be forwarded to the NIH/NINR Program Officer by the NCH IRB. In addition, reportable AEs and the IRB acknowledgement letter and cumulative reportable AEs, SAEs, and unanticipated problems will be forwarded to the NIH/NINR Program Officer with the PI's Annual Progress Report. .

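### A serious or Severe adverse event that the study team calls unrelated has no stated deadline to reach the DSMC other than the biannual report

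*Combined protocol and SAP*

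**What the plan says.** All of the relevant text is in Section 18.1 of the protocol.

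- Under Review of adverse events, the fast route is: "Possibly, probably, or definitely related AEs, as determined by the study team, will be reported within 24 hours to the DSMC chair".
- The same paragraph reserves the decision to the committee: "The DSMC will make the final determination on AE severity and relatedness".
- It also opens a wider route: "The study investigators will provide an initial review of all AEs to the DSMC". No time limit is attached to it.
- Under Identification of adverse events, study staff tell the PI of every event at once, and the PI "will include a description of AEs in the written report submitted biannually to the DSMC". Under Interim Monitoring Procedures: "All reports will be reviewed by the DSMC on a biannual basis". After each of those reviews the committee recommends whether the study goes on, changes or stops.
- The Definitions paragraph defines an SAE, and the grading scale defines Severe as decompensation that needs intubation or resuscitation. Neither term sets a deadline to the DSMC.

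**The concern.** The DSMC is meant to decide whether an event is related. Under the fast route, the study team's provisional answer to that same question determines whether the DSMC is told within a day. For mild events this is a sensible filter. For the gravest events it is weak, because those are the ones where an outside opinion on relatedness is worth most, and where a wrong provisional call costs most if it goes unchecked.

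At stake is whether the committee could act on such an event while infants are still being observed. If the only dated route is a periodic report, and that report falls after the last infant has been treated, the committee's final say protects nobody in this trial.

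**Working it through.** There is no sample-size, power or error-rate figure to reproduce. The check follows one event through every reporting route in Section 18.1, then compares the dated intervals with the enrolment period.

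**Step 1. Follow an SAE, or a Severe event, that the team calls unrelated.**

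| Route | Does it cover this event? | Deadline |
|---|---|---|
| Report to the DSMC chair | No; needs possible, probable or definite relatedness as judged by the team | 24 hours |
| Initial review of all events, to the DSMC | Yes | None stated |
| Biannual report to the DSMC | Yes | Next report |
| IRB, 5 business days | No; the event must also be related or probably related | Not applicable |
| IRB, annual continuing review | Not clearly; the list names "AEs that are not serious or unexpected" | Annual |
| Funder, with the annual progress report | Yes for SAEs, but does not go to the DSMC | Annual |
| Immediate report to the PI; monthly investigator meetings | Yes, or possibly, but neither is the DSMC | Immediate; monthly |

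Only two routes take this event to the DSMC. One has no date, and the other is the biannual report.

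**Step 2. Put days on the biannual report.** The protocol does not define biannual. Assume twice a year.

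- Interval between reports: 365 / 2 = 182.5, about 182 days.
- Wait for the scheduled report: from 0 to about 182 days, depending on where in the cycle the event falls.
- Wait for an event the team calls related: at most 1 day.

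**Step 3. Compare with the period in which infants are observed.**

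- Section 9.1 expects enrolment to take four months: 4 × 365 / 12 = 121.7, about 122 days.
- Section 6.2 places stress-response data collection between 10 and 20 days of life, so the last observation falls at most 20 days after the last enrolment: 122 + 20 = 142 days.
- If the first report comes one interval after the first enrolment (an assumption; no calendar is given), it arrives at about day 182, some 182 − 142 = 40 days after the last observation.
- If the calendar is not tied to the first enrolment, at most one report falls within the 142 days, because 142 is less than 182.

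**Step 4. Sensitivity.** With the first report at day 182, it would precede the last observation only if enrolment ran beyond about 182 − 20 = 162 days. A slower study therefore weakens the timing argument but leaves the maximum wait at about 182 days.

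**The case against.** Several stronger readings are tempting, and the documents do not support them.

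*The DSMC sees a grave event only if the team calls it related.* A reader might infer this from the 24-hour rule alone. The sentence on the initial review contradicts it: all events go to the DSMC. That review could arrive well before the biannual report. What stands is that it has no date, so nothing obliges it to.

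*Any alternative cause makes an event unrelated.* The definition of Unrelated does end with "the event does not follow a pattern of response and an alternative cause is present", and sick preterm infants often have other candidate causes. But the definition begins by requiring evidence that the event is definitely due to another cause, which is a stricter test. A timely event with no known pattern and a merely potential alternative cause fits none of the four categories cleanly, so its routing is uncertain rather than settled as unrelated.

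*A decompensation during the touch would escape the 24-hour rule.* Probably not in many cases. Section 15.1 lists bradycardia, apnea and desaturation as possible risks. A timely event along those lines, with a potential alternative cause, meets the definition of Probably Related and would go to the chair within 24 hours. The gap is confined to events the team attributes firmly to something else.

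*Filing with the IRB is held up by an open-ended DSMC review.* The 5-business-day limit largely bounds that review for events that qualify, so no change to IRB filing is called for.

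There are also fair points about weight. The protocol incorporates university, hospital, IRB and DSMC monitoring policies that are not reproduced, and one of them may already set an SAE deadline. The PI hears of every event at once. The study is small, the touch lasts 2.5 minutes, and SAEs are not expected. Nor does the point rest on whether the team is masked, since judging relatedness to a touch procedure ordinarily requires knowing whether the touch was given. These points lower the priority, but none supplies a deadline in the protocol itself.

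**Conclusion.** The point holds in a limited form. In Section 18.1 the 24-hour report depends on the study team's relatedness call and not on seriousness. An SAE or Severe event called unrelated therefore has no stated deadline to reach the DSMC other than the biannual report, although that committee makes the final call.

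The size is a longest dated wait of about 182 days against 1 day, with a scheduled report that could come some 40 days after the last infant is observed. This rests on three assumptions: biannual means twice a year, the first report follows the first enrolment by one interval, and enrolment takes the expected four months. It is a maximum, because the undated initial review may come sooner and policies outside the protocol may be stricter.

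This is a cheap improvement to safety oversight. It does not affect the trial's analysis or show that the DSMC would be kept uninformed.

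**What to change.** In Section 18.1, under Review of adverse events, add one sentence: every SAE and every event graded Severe is reported to the DSMC chair within 24 hours, regardless of the study team's attribution. Keep the present relatedness-based rule for lesser events.

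This brings the longest dated wait for such an event from about 182 days to 1 day. The cost is a small number of extra reports, near zero because the plan expects no SAEs. No new data collection is needed: every event already goes to the PI at once, so the added step is forwarding.

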19.0 Provisions to Protect the Privacy Interests of Subjects

- 19.1 Study staff will approach parents for infant recruitment only after they have visited the NICU to see their infant and received a medical update. Study staff will check with bedside caregivers in the NICU or the postpartum unit to ensure that it is an appropriate time to meet with parents. During the first meeting, study staff will ask parents if it is a good time to discuss their infant's eligibility for a research study. We will contact parents no more than three times for enrollment unless parents request additional meetings and will cease all recruitment efforts if parents indicate

that they are not interested in the study. We will access the minimum necessary PHI to determine infant eligibility.

We will provide unit education to all staff prior to the enrollment of infants so that nurses will be familiar with the study prior to any efforts to recruit individual nurses. To recruit individual nurses, study staff will approach nurses at the time of infant observation for an enrolled infant. We will cease all recruitment efforts if nurses indicate that they are not interested in participation.

- 19.2 We will fully explain all study procedures prior to participant enrollment and will remind parents and nurses that they may withdraw from the study at any time without penalty. We will provide participants with an explanation of our data safety procedures to code data with a SID. Although we will not be collecting sensitive data, we will inform parents of participating infants and nurse participants at the time of data collection that they may leave questions blank if they are not comfortable answering them.
- 19.3 Parents of participating infants will provide some data for their infants (i.e. demographic data) and will provide written HIPAA authorization included in the consent form for the study team to collect data from the EHR. Data to address Aim 2 will be collected directly from nurses.

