In a RCT, Co-I [name] tested the effect of a touch intervention provided during preterm infant feedings⁷⁵. Over 195 mean gavage feedings, infants in the experimental group received a touch experience on average 57% of the time versus 16% for infants in the control group; the touch varied from 6-15 minutes based on feeding duration. Importantly, some control group infants received no touch during feedings. Infants receiving greater amounts of touch achieved feeding milestones sooner⁷⁸ and had improved neurobehavior at discharge⁷⁹. These data demonstrate that comforting touch does not occur as part of routine caregiving, even though the frequency and essential nature of these activities would suggest their importance to optimal development⁸⁰. We will build on this work by measuring acute stress responses and standardizing the duration of touch.

3.3 The NaTI is a theory-guided, systematically delivered intervention provided during essential nursing care. The Neonatal Stress Embedding Model provides the theoretical foundation for this study and posits that NICU stress exposure activates the SAM pathway and HPA axis; repeated activation of these immature systems in the preterm infant results in aberrant programming, affecting brain structure and neurodevelopment³⁵. We will test the short-term effect of the NaTI on the stress response systems and will build on this work in a future study by examining the effect of routine implementation on neurodevelopment. We hypothesize that the NaTI will attenuate activation of the SAM pathway and HPA axis (Fig 1). To determine the effect, we will measure a broad spectrum of stress responses (HR, HRV, SRCs, cortisol), advancing the work of previous researchers who measured infant responses to specific procedures (e.g. heel lance^{51,62,63}, endotracheal suctioning^{62,64}) using a small number of biobehavioral measures. In contrast to other tested interventions, the NaTI requires no specialized training and a minimal time commitment (<5 minutes) from nurses and can be integrated as part of on-going essential care. The NaTI addresses how routine, necessary care is delivered. While the positive effects of comforting touch are well known, comforting touch is not a routine part of essential nursing care.

[figure not shown]

Figure 1. *Neonatal Stress Embedding Model*. Adapted from [name], [name], & [name]. (2019).

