5.0 Study Intervention/Investigational Agent

- 5.1 Description. The NaTI is a systematic touch intervention consisting of three static, brief touches provided by bedside nurses at specified points during essential care. To provide the NaTI, nurses will cradle the top of the infant's head with one hand, using their other hand to contain the infant's lower body. Nurses will provide the touch for one minute at the start of the care to allow infants time to acclimate to the stimulation, 30 seconds after the diaper change, and one minute at the conclusion of the care to provide a gradual end to the care and facilitate infant recovery and sleep. Nurses will provide the touches using bare hands (i.e. no gloves) to provide infants with human skin-to-skin contact and will perform hand hygiene before and after each touch. Nurses often provide discretionary comforting touch, commonly referred to as hand containment or facilitated tucking, in the same manner as the NaTI as part of their routine care (NCH Patient/Family Care Policy 30:23). The NaTI differs from discretionary comforting touch in that it is provided at specific points during the care and for a prescribed length of time. A member of the research team will be present during the care, perform timing for the intervention, and provide verbal instructions for nurses to begin and end the NaTI.

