6.0 Procedures Involved*

PROTOCOL TITLE: Pilot Study of Nurse-Administered Touch and Biobehavioral Stress Responses of Preterm Infants (Pilot NAT-BIO Study)

6.1 **Study Design. Aim 1.** Infants will be assigned to standard care or standard care with the addition of the NaTI in a randomized cross-over manner to determine the effect of a NaTI on biobehavioral stress responses during essential nursing care. We define essential nursing care as a scheduled episode of clustered caregiving activities related to health monitoring, hygiene, and clinical needs that includes at least a diaper change and feeding. We will enroll up to 20 infants for this pilot study to collect complete, usable data on 16 infants.

Aim 2. To identify factors to increase the feasibility of the NaTI as a nurse-administered, integrated part of essential, procedural care, we will conduct a survey study of nurses who have provided the NaTI to enrolled infants. We will specifically ask nurses to describe barriers and facilitators of implementation.

Aim 3. We will use a longitudinal cohort design to determine associations between biobehavioral responses and early neurobehavior. We will collect biobehavioral stress response data during the two observed episodes of care and will administer the NAPI to each enrolled infant at approximately 35 weeks PMA.

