risks and benefits, and the voluntary nature of participation and will inform parents that they may withdraw from the study at any time. Parents will have until their infant reaches two weeks of age to decide whether or not to participate in the study. For this minimal risk study, written informed consent will be required from one parent. If parents are unmarried without a paternity affidavit, consent will be obtained from the mother according to Ohio law.

Nurse participants. Prior to beginning infant enrollment, we will provide unit-based education for staff to introduce the intervention and the nursing survey study. Nurses will be individually approached at the time of infant observation. Study staff will provide an overview of the nursing survey study, including a discussion of the study purpose, surveys, potential risks, and the voluntary nature of the study. Nurses will have until the end of their shift to decide whether or not to participate in the study. At the time that consent is obtained, we will explain to nurses that they may be asked to complete additional surveys if they provide the NaTI again. They will be told at the time of consent and reminded, if they are asked to complete additional surveys, that study participation is completely voluntary. Study staff will further inform nurses that their decision to participate in the study will have no effect on their employment.

- 13.2 All infant participants will be hospitalized patients in the NCH NICUs. Nurse participants will be registered or licensed practical nurses employed in the NCH NICUs and providing care to infants receiving the NaTI.
- 13.3 Potential infant participants will be identified through periodic screening of the NICU census for recently admitted infants who meet inclusion criteria. Potential nurse participants will be identified during data collection for infants.
- 13.4 We will provide nurses employed in the NCH NICUs with an educational PowerPoint prior to the enrollment of infants. This PowerPoint will provide an overview of the study and will introduce nurses to the nursing survey study.
- 13.5 We will provide a small board book to participating infants at the time of the first observation and data collection. We will provide nurses with a \$10 Target gift card at the time of data collection each time they agree to complete a set of surveys.

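### Pre-enrolment education introduces the touch intervention to all unit staff, an avoidable and unmeasured risk that similar touch is added to the standard-care episodes

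*Combined protocol and SAP*

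**What the plan says.** Three places describe the education given before enrolment.

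- Section 19.1, on privacy and nurse recruitment: "We will provide unit education to all staff prior to the enrollment of infants so that nurses will be familiar with the study".
- Section 13.1, on recruiting nurses, says what it covers: "Prior to beginning infant enrollment, we will provide unit-based education for staff to introduce the intervention and the nursing survey study".
- Section 13.4 gives the form, a slide set: "This PowerPoint will provide an overview of the study and will introduce nurses to the nursing survey study".

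Section 6.1 sets the comparison: "Infants will be assigned to standard care or standard care with the addition of the NaTI in a randomized cross-over manner". Section 3.1 accepts that caregivers may be impossible to blind and relies on blinded outcome assessors and analysts.

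Section 5.1 describes the touch as already within these nurses' practice: "Nurses often provide discretionary comforting touch, commonly referred to as hand containment or facilitated tucking, in the same manner as the NaTI". What sets the NaTI apart is fixed points in the care and a prescribed duration. A member of the research team times it and tells the nurse when to begin and end. Section 3.3 says that "the NaTI requires no specialized training and a minimal time commitment".

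Section 6.2 records direct touches for the hour before the care episode. During the episode it records duration, procedures and procedural stressors. Comforting touch during the episode is not named. Section 25.2 gives one co-investigator oversight of intervention fidelity but describes no check on the standard-care condition.

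**The concern.** Every nurse who might give a standard-care episode belongs to the group that is to be introduced to the intervention. Those nurses already have the hold in their repertoire, so moving toward the NaTI on a standard-care day takes a prompt and no new skill. The plan supplies a possible prompt and nothing to counter it: no instruction to give care as usual, and no stated record of comforting touch during the observed episode.

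If such touch is added, the infant's actual exposure on the standard-care day changes. Blinded assessment and objective measures cannot correct that. The within-infant difference in heart rate, the primary outcome, and in the other responses would then be smaller than the effect of the NaTI against care as it was before the study. With 16 complete infants there is little reserve, and the attenuated estimate could be carried into the later study that Section 3.3 foresees.

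The route is avoidable. A researcher prompts delivery at the bedside and the plan says no specialized training is required, so the content of the touch need not be taught to the whole unit in advance.

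**Working it through.** **What the passages establish together**

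1. Who is educated: all staff, before infant enrolment (19.1).
2. On what: the intervention as well as the survey (13.1). Section 19.1 alone says only that nurses will know about the study, so this step rests on 13.1.
3. Who gives standard care: nurses on the same units, unblinded (3.1, 6.1).
4. What separates the conditions: three touches of 1 min + 0.5 min + 1 min = 2.5 min at set points, on a researcher's prompt (5.1). The hold itself is shared with existing practice.
5. What guards the standard-care episode: nothing that the documents describe.

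Steps 1 to 5 establish a risk. No passage establishes that the education changes what nurses do on standard-care days.

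**Illustration of what spill-over would cost**

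The documents give no alpha, power, effect size or standard deviation, so there is no planned figure to reproduce. The assumptions here are a two-sided 5% paired t-test, n = 16 pairs (the target for complete data in 6.1), and a share c of the NaTI effect that also reaches the standard-care episode.

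- Observed standardized difference: d(c) = d × (1 − c).
- Power: noncentral t with 16 − 1 = 15 degrees of freedom and noncentrality d(c) × √16 = 4 × d(c).
- Setting power to 80% at c = 0 gives d = 0.749. This value is solved from n = 16. It is not a claim about the true effect.
- The number of pairs needed to restore 80% power rises by about 1/(1 − c)². At c = 0.10 this is 1/0.81 = 1.23, and 16 × 1.23 = 19.7, so 20 pairs.

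| c | d(c) | Power at 16 pairs | Pairs for 80% |
|---|---|---|---|
| 0 | 0.749 | 80% | 16 |
| 0.035 | 0.723 | 77% | 18 |
| 0.10 | 0.675 | 71% | 20 |
| 0.16 | 0.630 | 65% | 22 |
| 0.25 | 0.562 | 56% | 27 |
| 0.28 | 0.540 | 52% | 29 |
| 0.50 | 0.375 | 29% | 58 |

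Three of these values borrow touch rates from the background section. The 0.035 is the cited share of nurse contacts that are comforting touch (3.1). The 0.16 and 0.28 come from the team's earlier feeding trial, in which "infants in the experimental group received a touch experience on average 57% of the time versus 16% for infants in the control group" (3.2): 0.16 is the control rate and 16/57 = 0.28 is the ratio. None of them estimates spill-over caused by staff education. The range runs from negligible to serious, and the documents cannot place the trial within it.

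**The case against.** The case against has force on several points.

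- **A reader might infer that the contrast is diluted toward no effect.** The documents do not support that. No passage shows that the education alters standard care. The direction is not fixed either: unblinded nurses could handle infants more gently on NaTI days, which would enlarge the contrast. Only the added-touch route acts toward zero.
- **A reader might infer that all staff are taught the hold, its timing and its expected benefit.** The slides are not in the documents, and 13.4 promises only an overview. What stands is that 13.1 names the intervention as a subject of the education and sets no limit on how much of it is shown.
- **A reader might take 16/57, and the 52% power that goes with it, as the expected loss.** That ratio comes from a different trial of touch during feeding, and the plan cites it to show how little comforting touch routine care contains. At the 3.5% background figure, power falls only from 80% to 77%.
- **Existing discretionary touch belongs to the declared comparator.** This is correct, and it should not be counted as contamination. The concern is limited to touch added because of the study.
- **Education has legitimate uses.** Section 25.2 plans nurse training. Advance familiarity also helps nurses who are approached on the day and have until the end of their shift to decide on the survey. These uses do not require the NaTI's time points, durations or hypothesised benefit to be shown to the whole unit beforehand.
- **Awareness cannot be removed entirely.** Nurses who have delivered the NaTI will know it and may later give a standard-care episode, and colleagues talk. This limits what the change can achieve but does not argue for adding a unit-wide route.

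**Conclusion.** The point holds as a risk of unknown size. The plan introduces the intervention to all staff before enrolment. It then relies on unblinded nurses from the same units for the comparator and gives them no instruction about discretionary touch. Touch added on standard-care days may attenuate the within-infant contrast, and the plan as described would neither prevent it nor show that it had occurred.

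The power figures rest on an assumed test, an effect solved from n = 16, and proportional spill-over from all causes. They show how sensitive 16 pairs would be and do not forecast the effect of a slide set. The case for acting is that the route is avoidable, the change is cheap, and it serves the aim in Section 3.1 of reducing performance bias.

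**What to change.** 1. In 13.1, 13.4 and 19.1, limit the pre-enrolment education to the study's purpose in general terms, logistics, monitoring electrodes, saliva collection and the nurse survey. Leave out the NaTI's time points, durations and hypothesised benefit.
2. In 5.1 or 6.2, state that the assigned nurse is instructed at the bedside on the NaTI day.
3. In 6.2, add one neutral instruction for standard-care days: provide care as usual.
4. In the context-of-care measures (6.2), have the research staff already at the bedside note the number, timing and duration of comforting touches during both observed episodes, and whether the nurse has previously delivered the NaTI. Report the achieved contrast in touch between conditions. For a pilot this is useful planning information whatever the cause of any overlap.

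The cost is an edit to the slide set and a few sentences of protocol text, a short addition to the observation form, and a few minutes of bedside instruction on each NaTI day (at most 20, one per enrolled infant). Nurses will have less advance familiarity when approached, and those who have already delivered the NaTI will remain aware of it.
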